3.3.4.2 Discontinuation of the trial by the sponsor

Boehringer Ingelheim reserves the right to discontinue the trial overall or at a particular trial site at any time for any of the following reasons:

1. New toxicological findings or serious adverse events invalidate the earlier positive benefit-risk-assessment. More specifically, the trial will be terminated if more than 50% of the subjects show drug-related and clinically relevant adverse events of moderate or severe intensity, or if at least one drug-related serious adverse event is reported.
2. The expected enrolment goals overall or at a particular trial site are not met
3. Violation of GCP, or the CTP, or the contract with BI by a trial site or investigator, disturbing the appropriate conduct of the trial
4. The sponsor decides to discontinue the further development of the investigational product.
5. Dose escalation will be stopped as soon as at least 2 subjects at one dose level on active drug showed relevant individual QT prolongation, i.e. a QTc increase of greater 60 ms from baseline in connection with absolute QT or QTc greater than 500 ms, which has been confirmed by a repeat ECG recording (e.g. follow-up ECG)
6. Dose escalation will be stopped based on preliminary PK results (plasma, see [Section 7.3.4](#)) as soon as measured (in at least one subject) or (upper limit of acceptable exposure in this trial, see [Section 2.1](#)). Further dose progression would be allowed only after a safety interim analysis and filing and approval of a pertinent protocol amendment.
7. Drug administration within a dose group and further dose escalation will be stopped if 3 or more of the subjects on active drug at the current dose level experienced vomiting of at least moderate intensity (see [Section 5.2.2.1](#) for definition of AE intensity)
8. Drug administration within a dose group and further dose escalation will be stopped if 2 or more of the subjects on active at one dose level experienced severe vomiting (see [Section 5.2.2.1](#) for definition of AE intensity)
- 9.

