- Preliminary measurement of BI 473494 plasma concentrations and preliminary determination of PK parameters (AUC, C_{max} , see [Section 7.3.4](#)). For the sake of caution, drug plasma concentrations of healthy male volunteers in this trial will be considered as a preliminary threshold (see [Section 2.1](#)). Further dose escalation beyond these thresholds would only be allowed after a safety interim analysis and filing and approval of a substantial CTP amendment.

Proprietary confidential information © 2017 Boehringer Ingelheim International GmbH or one or more of its affiliated companies

- An extensive safety laboratory will be performed with special focus on full blood exam (see time points in the [Flow Chart](#)).
- For safety reasons, each dose group of 8 subjects (6 on active, 2 on placebo) will be divided into 3 cohorts. The 1st and 2nd cohort will each comprise 2 subjects, the 3rd cohort will be a group of 4 subjects. Investigational drug administrations in these three cohorts will be separated by at least 72 hours (between 1st subject of each cohort), which is based on an anticipated median t_{max} of BI 473494 of 16-20 h (as derived from the median t_{max} of semaglutide in humans [[R17-0493](#)]) and median t_{max} of 32-40 h (as derived from the 6 weeks toxicology study in Cynomolgus monkeys [[n00253475](#)]) and is expected to cover the period of highest risk and peak pharmacodynamic effects. The first 2 cohorts will be dosed in a single blind, fixed sequence mode 'active – placebo' (1st cohort) and 'active – active' (2nd cohort). This design ensures that there is a time interval of at least 72 hours between first and second active dose of each dose level. This is expected to be sufficient to detect relevant acute effects of BI 473494. If BI 473494 was safe and well tolerated during the first administration, the remaining subjects of the respective dose level could be dosed as close as 10 minutes apart.
- A thorough ECG monitoring to cover the anticipated period of highest drug exposure with triple 12-lead ECGs over 29 Days following SC drug administration. Dose escalation would be stopped as soon as at least 2 subjects at one dose level showed relevant QT prolongation (see [Section 3.3.4.2](#) for details).
- Vital signs, body weight, aural body temperature will be assessed at time points given in the [Flow Chart](#).
- Although the risk of hypoglycaemic events is considered to be low for BI 473494 based on its mode of action

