For the inclusion or exclusion (see [Section 3.3](#)) of a subject and for the assessment of cardiac safety during the study, the QT and QTcB values generated by the ECG machines or their manual corrections by the investigators will be used. In doubtful cases, ECGs may be sent upfront for centralised evaluation (see below). In this case, these centrally measured results would overrule any other results obtained.

Abnormal findings will be reported as AEs (during the trial) or baseline conditions (at screening) if judged clinically relevant by the Investigator. Any ECG abnormalities will be monitored carefully and, if necessary, the subject will be removed from the trial and will receive the appropriate medical treatment.

A post-study centralised evaluation of the 12-lead ECGs recorded on Days 1 to 29 in Visit 3 will be performed by an independent ECG laboratory. This analysis will include the determination of cardiac axis as well as the intervals RR, PR, QRS and QT measured semi-automatically. Only the first of the three replicate ECGs at a single time point or at baseline will be evaluated. The remaining second and third replicate ECG will be stored for additional analysis if required, e.g. by authorities at a later time point.

For each QT interval, the RR interval preceding the QT will be measured to calculate the respective frequency corrected QTc intervals 'QTcF' according to Fridericia's formula ($QTcF = QT / RR^{1/3}$) and 'QTcB' according to Bazett's formula ($QTcB = QT / RR^{1/2}$). The QTcF correction will be used for evaluation and reporting. Abnormalities detected during centralised ECG evaluation will not necessarily qualify as AE. All interval measurements in one subject will be performed on the same lead. The intervals will be measured from four cardiac cycles (beats) in lead II. If lead II shows a flat T wave or is not measurable for any reason, lead V5 will be used, or if that lead is not measurable, then lead I will be used. The lead actually used will be reported in the CTR.

For blinding arrangements see [Section 4.1.6](#).

Assessed ECGs will comply with the ICH E14 guidance document and supplements [[R05-2311](#), [R13-0801](#), [R13-4095](#)] as well as the FDA requirements for annotated digital ECGs [[R09-4830](#)].

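### The QT stopping rule halts dose escalation but not dosing within the group, so cohort 3 can still receive a dose that has already met the QT threshold

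*Protocol*

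**What the plan says.** Protocol 3.3.4.2 lists the stopping rules.

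- **Criterion 5 (QT):** "Dose escalation will be stopped as soon as at least 2 subjects at one dose level on active drug showed relevant individual QT prolongation". A qualifying event is "a QTc increase of greater 60 ms from baseline in connection with absolute QT or QTc greater than 500 ms", confirmed by a repeat ECG.
- **Criterion 7 (vomiting of at least moderate intensity):** "Drug administration within a dose group and further dose escalation will be stopped if 3 or more of the subjects on active drug" are affected. Criterion 8 (severe vomiting, 2 or more active subjects) prescribes the same two actions.
- **Criterion 6 (exposure limit):** stops escalation only.
- **Criterion 1:** "the trial will be terminated if more than 50% of the subjects show drug-related and clinically relevant adverse events of moderate or severe intensity". A single SAE judged drug-related has the same consequence.

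Protocol 2.3 repeats the QT rule with the same single action: "Dose escalation would be stopped as soon as at least 2 subjects at one dose level showed relevant QT prolongation". The same section explains the staggering: "For safety reasons, each dose group of 8 subjects (6 on active, 2 on placebo) will be divided into 3 cohorts". The first subjects of successive cohorts are dosed at least 72 h apart. Protocol 7.5 fixes cohort 1 as one active and one placebo, cohort 2 as two active, and cohort 3 as 3:1.

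**The concern.** Criteria 7 and 8 name two separate actions, stopping dosing within the group and stopping escalation. Criterion 5 names only the second, so the first cannot be read into it. Followed as written, the QT rule lets cohort 3 receive the same dose after two of the first three active men have had confirmed, marked QT prolongation.

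The cohorts are staggered so that early findings can protect later subjects. For vomiting that protection is automatic. For QT it depends on someone's judgement or on how the events are classified. QT is also a named preclinical signal: Protocol 2.1 reports increased QTcR in monkeys at the highest exposure tested.

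**Working it through.** **Can the threshold be met before cohort 3?** Active subjects per cohort are 1 + 2 + 3 = 6, which matches the stated 6 active per group. Three are dosed before cohort 3 and three in it. The threshold is 2, so it can be met with cohort 3 undosed.

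**Would the data be in hand?** For on-study cardiac monitoring, "the QT and QTcB values generated by the ECG machines or their manual corrections by the investigators will be used" (Protocol 5.2.4.1), so the central reading need not be awaited. SAP Table 6.7: 1 lists post-dose ECGs at 6, 9, 12, 24, 28, 34, 48 and 60 h. That is 8 time points before the 72 h interval ends.

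**Does another visible rule stop cohort 3 automatically?**

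- *Safety review (Protocol 3.1).* It is mandatory before each dose escalation, and its data set should cover at least 6 subjects. Cohorts 1 and 2 total 4, so the scheduled review normally follows cohort 3.
- *First-administration condition (Protocol 2.3).* "If BI 473494 was safe and well tolerated during the first administration, the remaining subjects of the respective dose level could be dosed", with intervals down to 10 minutes. This governs spacing. Even if read as a gate, it would catch an event in subject 1 but not two events confined to cohort 2.
- *Criterion 1.* Two events are 2/3 = 67% of active subjects but 2/4 = 50% of all dosed, which is not more than 50%. The denominator is undefined. The events must also be judged drug-related, clinically relevant and at least moderate, or one must be classed as a drug-related SAE.
- *Investigator's power to stop dosing (Protocol 4.1.5), unscheduled reviews (3.1) and the sponsor's right to discontinue (3.3.4.2).* All are discretionary.

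**How often?** The documents give no QT event rate, so the risk p is an assumption, taken as constant and independent across active subjects.

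- A: met before cohort 3, P(≥2 of 3) = 3p²(1−p) + p³
- B: ever met in the group, P(≥2 of 6) = 1 − (1−p)⁶ − 6p(1−p)⁵
- C: both cohort 2 subjects and not subject 1 = (1−p)p²

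| p | A | B | A/B | C | C/B |
|---|---|---|---|---|---|
| 0.01 | 0.00030 | 0.00146 | 20% | 0.00010 | 6.8% |
| 0.05 | 0.00725 | 0.0328 | 22% | 0.0024 | 7.2% |
| 0.10 | 0.0280 | 0.1143 | 25% | 0.0090 | 7.9% |
| 0.20 | 0.104 | 0.3446 | 30% | 0.0320 | 9.3% |
| 0.30 | 0.216 | 0.5798 | 37% | 0.0630 | 10.9% |

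Example at p = 0.10: A = 3 × 0.01 × 0.9 + 0.001 = 0.028; C = 0.9 × 0.01 = 0.009. As p goes to 0, A/B tends to 3/15 = 20%, the number of pairs among 3 subjects over the number among 6.

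**The case against.** The strongest reply is that criterion 1 already covers most such cases. A confirmed QTc above 500 ms could well be judged an important medical event under Protocol 5.2.2.1 and, with plausible timing and no other cause, drug-related. One such report ends the whole trial, which is stricter than a two-subject rule. On this view vomiting needs its own within-group stop because it is expected pharmacology and might never be classed as serious. Criterion 6 is also escalation-only, so criterion 5 is not a lone slip.

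This narrows the gap but does not close it, because criterion 1 depends on medical classification and not on the QT threshold. The parallel with criterion 6 is weak: that rule uses preliminary PK, including AUC over 168 h, which cannot be complete within the 72 h between cohorts. ECGs, like vomiting, are seen as dosing proceeds.

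Three further points stand:

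- If the first-administration condition works as a gate, column C is the relevant one, and it is much smaller than A.
- Both columns are upper bounds for their p. They assume every event appears and is confirmed before cohort 3 is dosed, whereas ECGs continue to 672 h.
- Risks of 20% to 30% have no support in the documents. Men with repeated QTc above 450 ms, recent QT-prolonging drugs or Torsades risk factors are excluded, and exposure is capped with margins to the animal findings.

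Criterion 9 and the sponsor's list of always-serious events cannot be seen, and either might contain a relevant rule.

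**Conclusion.** The concern holds. No visible rule automatically withholds the dose from cohort 3 once two QT events are confirmed in cohorts 1 and 2, whereas criteria 7 and 8 do so for vomiting. What is missing is a mandatory trigger; the means to stop exist.

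When the threshold is met early, 3 of the 6 active subjects in the group are affected. The chance per dose group is 0.03% to 21.6% over assumed risks of 1% to 30%, or 0.01% to 6.3% if the 2.3 condition is taken as a gate. At risks of 1% to 5% the scenario is rare (0.03% to 0.7%, or 0.01% to 0.24%), but stopping rules are written for rare serious events.

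The change should be made, with medium confidence because of the unseen text. SAP section 4 records that escalation stopped after 75 µg, so the change now matters for any further dosing under this protocol or reuse of its wording.

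**What to change.** Give criterion 5 the same two actions as criteria 7 and 8, and make the same change in the QT bullet of Protocol 2.3. For example: *once at least two actively treated subjects at a dose level have confirmed QT prolongation as defined here, no further subject in that dose group is dosed and the dose is not escalated.* The threshold and the event definition stay as they are.

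The cost is one phrase in each place. It needs no extra subjects, assessments or time unless the rule is met. In that case the group may end with 3 instead of 6 active subjects.

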3.3.5 Replacement of subjects

In case that there are less than 4 subjects on active per dose level who complete the trial, the Trial Clinical Monitor together with the Trial Pharmacokineticist and the Trial Statistician are to decide if and how many subjects will be replaced. A replacement subject will be assigned a unique study subject number, and will be assigned to the same treatment as the subject he replaces.

4. TREATMENTS

4.1 TREATMENTS TO BE ADMINISTERED

The BI investigational product has been manufactured by BI Pharma GmbH & Co. KG. BI 473494 is administered as chloride salt and doses will be calculated as free peptide. The comparator product is commercially available.

4.1.1 Identity of BI investigational product and comparator product

The characteristics of the test product for doses up to 1.0 mg are:

Substance: BI 473494
Pharmaceutical formulation: Solution for injection
Source: BI Pharma GmbH & Co. KG, Germany
Unit strength: 1 mg/mL (1 mL per vial)
Route of administration: SC injection
Duration of use: Single dose

The characteristics of the test product for doses above 1.0 mg are:

Substance: BI 473494
Pharmaceutical formulation: Solution for injection
Source: BI Pharma GmbH & Co. KG, Germany
Unit strength: 10 mg/mL (1 mL per vial)
Route of administration: SC injection
Duration of use: Single dose

The characteristics of the comparator product (placebo) for all dose groups are:

Name: Isotone Natriumchloridlösung 0.9 % Braun Injektionslösung
Substance: Placebo containing sodium chloride 0.9 %
Pharmaceutical formulation: Solution for intravenous and SC injection
Source: B. Braun Melsungen AG, Germany
Unit strength: 0.9 %, 10 mL ampoule
Route of administration: SC injection
Duration of use: Single dose

4.1.3 Method of assigning subjects to treatment groups

Prior to the screening visit, subjects will be contacted in writing and informed about the planned visit dates. The subjects willing to participate will be recruited to dose groups according to their temporal availability. As soon as enough subjects have been allocated to one of the planned dose cohorts (3 cohorts per dose group), the following subjects will be allocated to one of the other dose cohorts. Therefore, the allocation of subjects to dose cohorts is not influenced by trial personnel, but only by the subjects' temporal availability. As the study includes healthy subjects from a homogenous population, relevant imbalances between the dose groups are not expected.

The randomisation list with study subject numbers and allocated treatments will be provided to the trial site in advance. The allocation of subjects to study subject numbers will be performed in Visit 2 prior to the first administration of trial medication. For this purpose, the subjects will be allocated to a study subject number by the method 'first come first served'. Once a subject number has been assigned, it cannot be reassigned to any other subject.

The randomisation procedure is described in [Section 7.5](#).

4.1.4 Selection of doses in the trial

For this trial, subcutaneous doses of BI 473494 in the range of 35 µg to 8.5 mg have been selected in order to assess safety and tolerability in healthy male volunteers, and to investigate pharmacokinetics of BI 473494. The doses selected cover a safe starting dose in the sub-therapeutic range, the therapeutic dose as well as supra-therapeutic dose below levels established by toxicological investigations and including a safety margin (see [Sections 1.2](#) and [2.3](#)).

4.1.5 Drug assignment and administration of doses for each subject

The treatments to be evaluated are outlined in [Table 4.1.5: 1](#) below. The dose volume for placebo corresponds to the dose volume of the respective dose level.

Table 4.1.5: 1 BI 473494 and placebo treatments, SC administration

Dose group	Substance	Pharmaceutical form	Unit strength	Dose volume per administration (single dose)	Total dose
1	BI 473494	Solution for injection	1 mg/mL	35 µl = 0.035 mL	35 µg
2	BI 473494	Solution for injection	1 mg/mL	75 µl = 0.075 mL	75 µg
3	BI 473494	Solution for injection	1 mg/mL	150 µl = 0.15 mL	150 µg
4	BI 473494	Solution for injection	1 mg/mL	300 µl = 0.3 mL	300 µg
5	BI 473494	Solution for injection	1 mg/mL	550 µl = 0.55 mL	550 µg
6	BI 473494	Solution for injection	1 mg/mL	1000 µl = 1.0 mL	1.0 mg
7	BI 473494	Solution for injection	10 mg/mL	160 µl = 0.16 mL	1.6 mg
8	BI 473494	Solution for injection	10 mg/mL	260 µl = 0.26 mL	2.6 mg
9	BI 473494	Solution for injection	10 mg/mL	400 µl = 0.4 mL	4.0 mg
10	BI 473494	Solution for injection	10 mg/mL	600 µl = 0.6 mL	6.0 mg
11	BI 473494	Solution for injection	10 mg/mL	850 µl = 0.85 mL	8.5 mg
1-11	Placebo*	Solution for injection	--	identical to active treatment	--

* Subjects receiving placebo are equally distributed across dose groups

The syringes containing the SC solutions for administration (BI 473494 or placebo) will be prepared by pharmacists, qualified pharmacy staff members or qualified medical study personnel at the trial site under the responsibility of the Investigator. The Investigator can decide at any time to stop dosing or (after consultation with the Sponsor) to decrease the dose escalation by adding intermediate doses in case of intolerance or safety concerns.

The trial medication BI 473494 or placebo will be administered to subjects on Day 1 of Visit 3 (at time-point 0:00) by SC injection into a lifted skin fold of the abdominal wall by the investigating physician or an authorised designee while subject lies in semi-upright position. Skin is sanitized prior to injection. Size of syringes used for administration is dependent on administered volume (e.g. BD Micro-Fine™ + Demi 0.3 mL with 8 mm needle attached or

Proprietary confidential information © 2017 Boehringer Ingelheim International GmbH or one or more of its affiliated companies

1 mL Inject[®]-F/Inject[®], B. Braun Melsungen, Germany with hypodermic needles for SC injection (30G x 12 mm or 30G x 13 mm). For lower volumes using BD Micro-FineTM + Demi syringes and higher volumes using 1 mL Inject[®]-F/Inject[®] syringes, the injection needle has to be placed at a 90 degree or 45 degree angle, respectively. Injection of trial medication into the skin fold has to be performed over at least 15 seconds. For volumes higher than 1.0 mL, dose will be split into two injections. Following SC injection, the subject should remain in a semi-upright position for at least 30 minutes. Injection site will be marked by a pen.

The so-called four-eye principle (two-person rule) should be applied for administration of trial medication and – if applicable – its preparation, if correct dosage cannot be ensured otherwise.

Administration of BI 473494 or placebo will be performed by the Investigator or an authorized designee following an overnight fast, which is to start no later than 10 h before the scheduled dosing. Water may be consumed ad libitum except for 1 hour before and 1.5 hours after drug administration. Standardised meals will be served as outlined in the [Flow Chart](#). For restrictions with regard to diet see [Section 4.2.2.2](#).

Subjects will be kept under close medical surveillance until 72 h following investigational drug administration. Thereafter, the trial will be performed in an ambulatory fashion.

4.1.6 Blinding and procedures for unblinding

4.1.6.1 Blinding

The treatments administered will be blinded to subjects only (single-blind). With the rising dose design, single-blind conditions regarding the subjects' treatment (active or placebo) are maintained within each dose group, however the current dose level will be known to subjects and investigators.

The database of this trial will be handled in an open-label fashion, because no bias with regard to data cleaning of safety measures is expected. This is considered acceptable because the potential for bias seems to be low and does not outweigh practical considerations.

The Bioanalyst of the analytical laboratory, the Trial Pharmacokineticist and the Trial Pharmacometrist may receive the randomisation codes prior to official unblinding to perform preliminary PK analyses. He or she will treat the codes confidentially.

In addition, the Drug Metabolism Scientist may receive the randomisation codes prior to official unblinding to perform metabolites in safety testing analysis (MIST). He or she will confirm in writing that the codes will be treated confidentially.

Within the ECG laboratory, the staff involved with interval measurements and assessments will be blinded with respect to the treatment within each dose level and also with regard to the recording date and time as well as time the points of the ECGs. The interval measurements for a given subject will be performed in a random and blinded sequence by a single technician. No more than two different blinded readers will evaluate the ECGs of the study.

Proprietary confidential information © 2017 Boehringer Ingelheim International GmbH or one or more of its affiliated companies

4.1.6.2 Procedures for emergency unblinding

As this trial will be conducted single-blinded, the treatment information will be known. Therefore, no emergency envelopes will be provided.

4.1.7 Packaging, labelling, and re-supply

4.1.7.1 BI 473494

Vials containing BI 473494 will be provided by the Department of Pharmaceutical Development of Boehringer Ingelheim Pharma GmbH & Co. KG, Biberach, Germany.

The clinical trial supply consists of containers holding the trial medication which are labelled with trial identification. The required information according to the German Drug Law as well as Annex 13/EU GMP Guideline will be provided on the containers. Smaller boxes within the clinical trial supply containers will be labelled with:

- BI trial number
- Name of product and strengths or identification code
- Pharmaceutical dosage form, quantity of dosage units
- Route and mode of administration
- Term 'For Clinical Trial Use' (domestic language)
- Sponsor name and address
- Storage conditions
- Use-by date
- Batch number

Vials will be labelled with the reduced requirements.

The telephone number of the Sponsor and name, address and telephone number of the trial site are given in the subject information form. The EudraCT number is indicated on the title page of this protocol as well as on the subject information and informed consent forms. Examples of the labels will be available in the ISF.

Considering the short shelf life of BI 473494 solution for injection, it is planned to send the trial medication to the site in several fractions.

